This amended protocol 03 (amendment 3) is considered to be non substantial based on the criteria set forth in Article 10(a) of Directive 2001/20/EC of the European Parliament and the Council of the European Union.

OVERALL RATIONALE FOR THE AMENDMENT

The overall rationale for the changes implemented in the protocol amendment is to add an interim analysis to determine if efficacy in the primary endpoint of annualized rate of moderate or severe chronic obstructive pulmonary disease (COPD) exacerbations is met at the time of the interim analysis, as COPD is a disease with a high unmet medical need. The interim analysis will be performed when $\geq 92\%$ of the information fraction for the primary endpoint is available, but prior to all patients completing the 52-week treatment period.

Protocol amendment summary of changes table

Section # and Name	Description of Change	Brief Rationale
Section 1.1 Synopsis	Added a bullet on an interim analysis.	Interim analysis is planned for efficacy as COPD is a disease with high unmet medical need.
	Update of the data monitoring committee activities.	Update
Section 8.3.8 Disease- related events and/or disease-related outcomes not qualifying as AEs or SAEs	Deletion of "and thus will not be considered unexpected condition" and "Any other AE not listed as an expected event in the IB or in this protocol will be considered unexpected".	For accuracy and to clarify the current process.
Section 9.2 Sample Size Determination	Added details on alpha value at final analysis.	Interim analysis is planned for efficacy.

Section # and Name	Description of Change	Brief Rationale
Section 9.4 Statistical Analyses	Clarified the statistical analysis plan (SAP) will be finalized before the interim analysis.	Interim analysis is planned for efficacy.
Section 9.4.1 Efficacy analysis	Added details that if the primary endpoint is positive at the interim analysis, Week 52 endpoints will be analyzed using participants who had the opportunity to reach Week 52 at the time of the IA cut-off date.	Interim analysis is planned for efficacy.
	Update of the Statistical Analysis Methods wording for exploratory endpoints.	Clarification
Section 9.4.1.1 Multiplicity Considerations	Added details on the Kim-DeMets spending function for the interim analysis and hierarchical procedure for multiple endpoints.	Interim analysis is planned for efficacy.

1 PROTOCOL SUMMARY

1.1 SYNOPSIS

Protocol title:

A Randomized, Double-blind, Placebo-controlled, Parallel-group, 52-week Pivotal Study to Assess the Efficacy, Safety, and Tolerability of Dupilumab in Patients with Moderate-to-severe Chronic Obstructive Pulmonary Disease (COPD) with Type 2 inflammation

Short title:

Pivotal study to assess the efficacy, safety and tolerability of dupilumab in patients with moderate-to-severe COPD with Type 2 inflammation (NOTUS)

Rationale:

Chronic obstructive pulmonary disease (COPD) is a highly prevalent disease worldwide, associated with significant economic burden, and for which available standard-of-care therapy shows insufficient treatment effect on symptoms, lung function, exacerbations and long-term evolution of the disease. Though the inflammatory component in COPD is typically thought to be neutrophilic, there has been an identified subgroup of COPD which is characterized by a concomitant elevation in blood eosinophils which suggests a Type 2 inflammatory component of the disease in these patients. This study is designed to investigate the efficacy and safety of dupilumab over one year in patients with COPD with Type 2 inflammation who are in need of an additional treatment added to their current management. The presence of a placebo arm is appropriate for the objectives of this study, since it will provide the most robust assessment of the efficacy and safety of dupilumab. All patients will receive standard of care background medication throughout the study. The proposed study design provides the opportunity to assess the efficacy of dupilumab on multiple COPD domains including lung function, prevention of moderate and severe exacerbations, and symptom control. The effect on lung function and symptom control will be evaluated over both the short and long term.

Objectives and endpoints

Objectives Endpoints Primary To evaluate the efficacy of dupilumab 300 mg Annualized rate of moderate* or severe** COPD exacerbations over q2w in patients with moderate or severe the 52-week treatment period compared to placebo. COPD as measured by *Moderate exacerbations are recorded by the Investigator and Annualized rate of acute moderate defined as AECOPD that require either systemic corticosteroids or severe COPD exacerbation (such as intramuscular, intravenous or oral) and/or antibiotics. (AECOPD). **Severe exacerbations are recorded by the Investigator and defined as AECOPD requiring hospitalization, or observation for >24 hours in an emergency department/urgent care facility or resulting in death. For both moderate and severe events to be counted as separate events, they must be separated by at least 14 days.

Objectives	Endpoints
Key secondary	
To evaluate the effect of dupilumab 300 mg q2w on	 Change in pre-bronchodilator FEV₁ from baseline to Week 12 compared to placebo.
 Pre-bronchodilator forced expiratory volume in 1 second (FEV₁) over 12 weeks compared to placebo. Health related quality of life, assessed by the change from baseline to Week 52 in the St. George's Respiratory Questionnaire (SGRQ). Pre-bronchodilator FEV₁ over 52 weeks compared to placebo. 	 Change from baseline to Week 52 in SGRQ total score compared to placebo. Proportion of patients with SGRQ improvement ≥4 points at Week 52. Change in pre-bronchodilator FEV₁ from baseline to Week 52 compared to placebo.

Overall design:

Multinational, randomized, double-blind, placebo-controlled, parallel group (2 groups), 52-week, pivotal Phase 3 study to assess the efficacy, safety, and tolerability of dupilumab in patients with moderate-or-severe COPD with Type 2 inflammation such as that driven by activation of IL-4, IL-5, and IL-13 on an established long acting beta-agonist (LABA), long acting muscarinic antagonist (LAMA) and/or inhaled corticosteroid (ICS) background therapy (triple therapy unless ICS contraindicated). Study treatments are dupilumab 300 mg q2w or placebo q2w administered during the 52-week randomized treatment period. The study includes 3 study periods.

- Screening (4 weeks ± 1 week).
- Randomized investigational medicinal product (IMP) treatment period (52 weeks ±3 days).
- Post IMP treatment period (12 weeks ± 5 days).

Patients who satisfy the inclusion and exclusion criteria will be randomized (1:1) to one of the following IMP treatment groups to be administered for 52 weeks.

- Dupilumab 300 mg, administered as 1 subcutaneous (SC) injection q2w.
- Placebo, administered as 1 SC injection of placebo matching dupilumab.

Randomization will be stratified by country, ICS dose (high dose ICS [yes/no]) at baseline, and smoking status at screening (current smokers or not). Enrollment will be capped at 30% current smokers (as defined by smoking status at screening visit).

Treatment discontinuation follow-up:

Patients who discontinue the study treatment prematurely (prior to completing the 52-week treatment period) will perform, as soon as possible, the early treatment discontinuation (ETD) visit with all assessments normally planned for the end of treatment (EOT) visit, to assure a complete clinical assessment in close temporal proximity to the premature termination of study treatment is available. In addition, to allow assessment of patient outcomes over the stipulated

study period, patients will be asked and encouraged to complete all remaining study visits, and participate in all safety follow-up assessments according to the visit schedule. For these patients the assessment schedule will be reduced (see Section 1.3.2) and visits during the planned treatment period may be conducted by phone (except for planned EOT) if patient is unable to come in for a site visit. Assessments not completed via phone should be performed at the next scheduled visit. For further details please see Section 7.1.1.

Post-IMP treatment follow-up

Upon completing the 52-weeks randomized IMP treatment period, patients will continue their background ICS/LABA/LAMA therapy and enter the 12-week safety follow-up period. Adjustment of background medication is allowed at the discretion of the Investigator as clinically indicated during the post-treatment period (see Section 6.1.2 for further details).

Disclosure Statement: This is a Parallel Treatment study with 2 arms that is blinded for patients and the Investigator.

Number of participants:

Approximately 924 patients are planned to be randomly assigned to study intervention for an estimated total of 462 evaluable patients per intervention group (see Section 9.2).

Intervention groups and duration:

Study participation for each patient will be a total of approximately 69 weeks including up to 5 weeks for screening, 52 weeks of IMP treatment period and 12 weeks of follow-up.

Study intervention(s)

Investigational medicinal products.

- Dupilumab 300 mg.
 - Formulation: Dupilumab 300 mg for SC administration is supplied as 150 mg/mL solution in 2.25 mL prefilled glass syringes to deliver 300 mg in 2 mL.
 - Route of administration: subcutaneous injection. All IMP applications will be done as separate injections into different injection sites.
 - Dose regimen: dupilumab 300 mg q2w administered as 1 SC injection.
- *Matching Placebo for dupilumab.*
 - Formulation: Placebo matching dupilumab will be supplied as an identical formulation to the active formulation but without dupilumab.
 - Route of administration: subcutaneous injection. All IMP applications will be done as separate injections into different injection sites.
 - Dose regimen: Placebo administered as 1 SC injection of placebo matching dupilumab 300 mg (2 mL).

Noninvestigational medicinal products(s)

Background therapy

Patients should continue the regular administration of their previous standard of care background therapy for COPD throughout the study, including:

Triple therapy: ICS + LABA + LAMA (Double therapy: LABA + LAMA allowed if ICS is contraindicated)

- Formulation: dry powder inhaler (DPI), metered dose inhaler (MDI) or pocket nebulizer.
- Route(s) of administration: Oral inhalation.
- Dose regimen: As prescribed.
- Background medication should not be adjusted during Screening. Patients are strongly
 encouraged to maintain their background therapy for the entire duration of their treatment
 therapy. After 1 severe or 2 moderate exacerbations of COPD, dose adjustments in
 background therapy, if required will be permitted for symptom control and as needed for
 the remainder of the trial period.

Reliever medication

- Patients may use albuterol/salbutamol or levalbuterol/levosalbutamol (including ipratropium or ipratropium/short acting β-agonist [SABA] combinations or terbutaline) as reliever medications as needed during the study.
- Formulation: MDI, nebulizer solutions or DPI.
- Route of administration: oral inhalation.
- Dose regimen: as prescribed.

Statistical considerations:

- Analysis populations
 - The efficacy population will be the intention-to-treat (ITT) population, defined as all randomized patients analyzed according to the treatment group allocated by randomization.
 - The safety population will include all patients who actually received at least one dose or a partial dose of the IMP, analyzed according to the treatment actually received.
- **Primary analysis:** The annualized rate of moderate or severe COPD exacerbation events will be analyzed using a negative binomial regression model. The model will include the total number of events occurring during the 52-week treatment period as the response variable, with the treatment group, region (pooled country), ICS dose (high dose ICS [yes/no]), smoking status at screening (current smokers or not), baseline disease severity (as % predicted post-bronchodilator FEV₁), and number of moderate or severe COPD exacerbation events within one year prior to the study (≤2, 3, or ≥4) as covariates. Log-transformed observation duration will be used as offset variable. Patients who permanently discontinue the study treatment will be encouraged to complete the study as planned and the additional off-treatment exacerbation events up to Week 52 will be

included in the primary analysis. Sensitivity analyses for handling missing data may include pattern mixture model by multiple imputation and tipping point analyses.

• Analysis of key secondary endpoints:

The change from baseline in pre-bronchodilator FEV₁ at Week 12 will be analyzed using mixed-effect model with repeated measures (MMRM). The model will include change from baseline in FEV₁ values up to Week 12 as response variables, and factors for treatment group, age, sex, baseline height, region (pooled country), ICS dose (high dose ICS dose [yes/no]), smoking status at screening (current smokers or not), visit, treatment-by-visit interaction, baseline pre-bronchodilator FEV₁, and FEV₁ baseline-by-visit interaction as covariates. An unstructured correlation matrix will be used to model the within-patient errors. Parameters will be estimated using restricted maximum likelihood method using the Newton-Raphson algorithm. For patients discontinued the study treatment, off-treatment FEV₁ values will be included in the analysis. Sensitivity analyses for handling missing data may include pattern mixture model by multiple imputation and tipping point analyses.

The change from baseline in pre-bronchodilator FEV₁ at Week 52 will be analyzed in a similar way as change from baseline in pre-bronchodilator FEV₁ at Week 12 and the model will include values up to Week 52 as response variables.

The change from baseline in SGRQ total score at Week 52 will also be analyzed in a similar way except that the MMRM model will include the following covariates: treatment group, region (pooled country), ICS dose (high dose ICS [yes/no]), smoking status at screening (current smokers or not), visit, treatment-by-visit interaction, baseline SGRQ total score, and SGRQ baseline-by-visit interaction.

The proportion of patients with SGRQ improvement ≥4 points at Week 52 will be analyzed using a logistic regression model. The model will include treatment group, region (pooled country), ICS dose (high dose ICS [yes/no]), smoking status at screening (current smokers or not), and baseline SGRQ total score as covariates. Patients with missing SGRQ total score at Week 52 will be considered as non-responders.

[figure not shown]
- **Multiplicity considerations:** Multiplicity is considered for testing multiple endpoints. The overall type-I error rate will be controlled at the two-sided 0.05 level. Details will be provided in Section 9.4.1.1.
- **Safety analyses:** The safety variables, including adverse events (AEs), laboratory parameters, vital signs, electrocardiography, and physical examinations will be summarized using descriptive statistics.
- An interim analysis will be performed during the study. See Section 9.5 for further details.

Data Monitoring Committee: Yes

• A data monitoring committee (DMC), independent from Sponsor, will be established for this study. This committee is comprised of externally-based individuals with expertise in the diseases under study, biostatistics, or clinical research. The primary responsibilities of the DMC are to review and evaluate the safety and efficacy data during the course of the trial, review interim analysis results and make appropriate recommendations regarding the conduct of the clinical trial to the Sponsor.

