Total IgE		Х	$ldsymbol{ld}}}}}}$					X																				X		 	X
Fibrinogen		Х		$ldsymbol{ldsymbol{ldsymbol{eta}}}$		_								X	\Box					$ldsymbol{ldsymbol{ldsymbol{eta}}}$								Χ		└	X
Whole blood RNA (optional)		X												X														х			
DNA (optional)		Χ ^p]
Serum/plasma for archival samples (optional)		х		x				х						х						х								Х			

	Screening	Randomization/ Baseline																													
VISIT	1	2 ^{a,b}	3	4		5		6		7 ⁸		8 ^S		9		10 ⁸		11 ⁸		12		13 ⁸		14		15 ⁸		16 ^C	17 ⁸	18 ^S	19
WEEK ^a	W-4 to W0	0	2	4	6	8	10	12	14	16	18	20	22	24	26	28	30	32	34	36	38	40	42	44	46	48	50	52 (EOT)	56	60	64 (EOS)
Efficacy																															
COPD exacerbation reporting by the Investigator		х	х	x		x		x		x		х		x		X		х		x		x		x		x		х	x	x	x
Spirometry (pre-BD) ^{m,n}	X	х	х	х		x		x						х						х				X				Х			Х
Spirometry (post-BD) ^{m,n}	х	х	х	х		x		x						х						х								Х			х
EXACT ^g	Every day (d	liary) from screening	to W	eek 5	2																										
SGRQ ^g		х		Х				X						X						Х								X			Х
EQ-5D-5L ^g		Х												Х														X			
Health care utilization ^q		х		x		x		X		х		х		X		X		х		х		X		X		Х		Х			х

β-hCG = Human chorionic gonadotropin-beta; BD = bronchodilator; BID = twice daily assessments; BODE= Body-mass index, airflow Obstruction, Dyspnea, and Exercise; continuous = subsequent visits during the treatment period; COPD = chronic obstructive pulmonary disease; cont. = continuous; CT = computed tomography, DNA = Deoxyribonucleic acid; ECG = Electrocardiogram, EDTA = Ethylenediaminetetraacetic acid; EOS = End of Study; EOT = End of treatment; EQ-5D-5L = Euro Quality of Life-5 Dimension 5-Level questionnaire; EXACT = Exacerbations of COPD tool; FeNO = Fractional exhaled nitric oxide; HBV = hepatitis B virus, HCB = hepatitis C virus, HIV = human immunodeficiency virus; IgE = Immunoglobulin E; IMP = Investigational Medicinal Product; IVRS = Interactive Voice Response System; IWRS = Interactive Web Response System; LABA = Long-acting β2 agonists; LAMA = Long-acting muscarinic antagonist; mMRC = Modified Medical Research Council Dyspnea Scale; PARC = Pulmonary and activation-regulated chemokine:

PGX = pharmacogenetic; PK = Pharmacokinetic; RNA = Ribonucleic acid; SABA = Short-acting β-agonists; SAEs = Serious adverse events; SC = subcutaneous; SGRQ = St. George's Respiratory Questionnaire.

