- m Spirometry will be done locally according to European Respiratory Society (ERS)/American Thoracic Society (ATS) 2005 guidance but measured by a central laboratory. Spirometry will be performed during a trough period of bronchodilators according to their action duration, for example, withholding the last dose of salbutamol/albuterol or levosalbutamol/levalbuterol for at least 6 hours, withholding the last dose of ipratropium for at least 8 hours, withholding the last dose of LABA for at least 12 hours (ultra-long acting LABA like vilanterol should be withheld for at least 24 hours) and withholding the last dose of LAMA for at least 24 hours. This will be verified before performing the measurements. Note: When both pre- and post-bronchodilator spirometry is assessed, the post-bronchodilator spirometry should be performed consistent with the mechanism of action of reliever (ie, 30 minutes for albuterol or other SABA). See Section 8.1.1.2 for details.
- n Following randomization and during the treatment period if spirometry is not performed at the scheduled visit it should be performed at the following on-site visit for all visits prior to Week 12. If not performed at Week 12 or at subsequent scheduled on-site visits, an unscheduled assessment is required within 3 weeks of the missed scheduled.
- o PK and ADA samples to be collected prior to the administration of the drug.
- p If collection is not completed at randomization, sample can be taken at a following visit.
- q Includes collection of sick days, lost usual activities, and additional physician visits or other health care utilization.
- r To be completed prior to IMP administration.
- s Telephone visit.

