8.1.1.2 Spirometry

Spirometry at clinical site visits should be performed in accordance with the European Respiratory Society (ERS)/American Thoracic Society (ATS) guidelines (22) and prior to administration of investigational product.

For pre-bronchodilator measured parameters, including FEV₁, FVC and forced expiratory flow (FEF) 25%-75%, spirometry will be performed after a wash out period of bronchodilators according to their action duration, for example, withholding the last dose of salbutamol/albuterol or levosalbutamol/levalbuterol for at least 6 hours, withholding the last dose of LABA for at least 12 hours (ultra-long acting LABA like vilanterol should be withheld for at least 24 hours), withholding the last dose of ipratropium for at least 8 hours and withholding the last dose of LAMA for at least 24 hours. This will be verified before performing the measurements.

Note: When both pre- and post-bronchodilator spirometry is assessed, the post-bronchodilator spirometry should be performed consistent with the mechanism of action of reliever (ie, 30 minutes for albuterol or another SABA).

At all visits, spirometry will be performed preferably in the morning; afternoon/evening is allowable in the exceptional circumstance when morning spirometry cannot be performed; spirometry should be done at approximately the same time at each visit throughout the study. Current smokers need to be reminded not to smoke for at least 1 hour before spirometry. The same spirometer and standard spirometric techniques, including calibration, will be used to perform spirometry at all visits and, whenever possible, the same person should perform the measurements.

Three measurements fulfilling the ATS acceptability and repeatability criteria should be obtained at every visit, if possible.

Further details on spirometry will be available in a separate operational manual provided to the sites.

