2 STATISTICAL AND ANALYTICAL PROCEDURES

2.1 ANALYSIS ENDPOINTS

2.1.1 Demographic and baseline characteristics

The baseline value of efficacy parameters is defined as the last available value up to randomization but prior to the first dose of study medication unless otherwise specified. The baseline value of the other parameters is defined as the last available value prior to the first dose of investigational medicinal product (IMP) if the patient is treated, or the last available value up to randomization if the patient is not exposed to IMP.

The calculation of the baseline for daily ediary questionnaire scores will be specified in [Section 2.1.3.2.2.1](#).

All baseline safety and efficacy parameters (apart from those listed below) will be presented along with the on-treatment summary statistics in the safety and efficacy sections ([Section 2.4.5](#) and [Section 2.4.4](#)).

Demographic characteristics

Demographic variables are:

- Gender (Male, Female),
- Race (Caucasian/White, Black/of African descent, Asian/Oriental, American Indian or Alaska Native, Native Hawaiian or other Pacific Island, Unknown)
- Ethnicity (Hispanic or Latino, Not Hispanic or Latino, Unknown)
- Age in years (quantitative and qualitative variable: 40-64, 65-74, 75-80, 81-85 years)
- Region (Latin America: Argentina, Colombia, Peru, Chile, Brazil and Mexico; East Europe: Russia, Ukraine, Poland, Bulgaria, Lithuania, Latvia, Czech Republic, Slovakia, Hungary, Romania, Serbia; Western Countries: Australia, Belgium, France, Portugal, Spain, Germany, Netherlands, United Kingdom, South Africa, Canada, USA, Greece)
- Territory (North America: Canada and USA; European Union: Belgium, Poland, Bulgaria, Spain, France, Portugal, Germany, Netherlands, Lithuania, Latvia, Greece, United Kingdom, Czech Republic, Slovakia, Hungary, Romania; Rest of World: Australia, South Africa, Argentina, Chile, Colombia, Peru, Brazil, Mexico, Russia, Ukraine, Serbia)
- Weight in kg (quantitative and qualitative variable: <50, 50-<100, ≥100 kg)
- BMI in kg/m² (quantitative and qualitative variable: <25, 25-<30, 30-<35, ≥35 kg/m²)

Medical or surgical history

Medical (or surgical) history includes all the relevant medical (or surgical) history during the lifetime of the patient.

This information will be coded using the version of Medical Dictionary for Regulatory Activities (MedDRA) currently in effect at Sanofi at the time of database lock.

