First, missing values will be imputed by PMM-MI as illustrated above. The imputed values in placebo group will then be shifted by adding a sequence of positive values and the imputed values in dupilumab group will be shifted by subtracting a sequence of positive values. For each combination of the shift parameters, each of the imputed and shifted datasets will be analyzed with the ANCOVA model and their results will be combined using Rubin's formula to generate statistical inference. LS mean difference between dupilumab and placebo in change from baseline in pre-BD FEV₁ at Week 12 and the corresponding p-values will be provided for each combination of shift parameters.

More details of the imputation and analyses methods are included in Appendix K.

2.4.4.2.2 Analysis of the change from baseline in pre-bronchodilator FEV₁ and SGRQ total score and domain scores at Week 52 for dupilumab versus placebo

The change from baseline in pre-bronchodilator FEV₁ at Week 52 will be analyzed in a similar way as change from baseline in pre-bronchodilator FEV₁ at Week 12 and the model will include values up to Week 52 as response variables. The analysis will be performed in the full ITT population and also in the baseline FeNO ≥ 20 ppb subgroup.

The change from baseline in SGRQ total score and domain scores at Week 52 will be analyzed in a similar way as change in pre-bronchodilator FEV₁ at Week 52 except that the MMRM model will include the following covariates: treatment group, region (pooled country), ICS dose at baseline (high dose ICS [yes/no]), smoking status at screening (current smokers or not), visit, treatment-by-visit interaction, baseline SGRQ total score, and SGRQ baseline-by-visit interaction.

Descriptive statistics including number of patients, mean, standard error, and least squares (LS) means will be provided. In addition, difference in LS means and the corresponding 95% confidence intervals (CI) will be provided along with the p-values.

2.4.4.2.3 Analysis of proportion of patients with SGRQ improvement ≥ 4 points at Week 52 dupilumab versus placebo

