Step 3. Each of the 40 complete datasets will be analyzed using an ANCOVA model with change from baseline in pre-BD FEV₁ at Week 12 as the response variable, treatment, age, sex, height, region (pooled country), ICS dose at baseline (high dose ICS [yes/no]), smoking status at screening (current smokers or not), and baseline pre-BD FEV₁ value as covariates. Then the SAS MIANALYZE procedure will be used to generate statistical inferences by combining results from the 40 analyses using Rubin's formula.

- ***Tipping point analysis***

Step 1. 40 imputations will be performed to generate 40 completed data sets following Step 1 and 2 for PMM-MI.

Step 2. The imputed FEV₁ values in Dupilumab group are subtracted by a positive amount d for each imputed data sets.

Step 3. The imputed FEV₁ values in placebo group are added by a positive amount p for each imputed data sets.

Step 4. Change from baseline in pre-BD FEV₁ will be analyzed using the ANCOVA model as described in the PMM-MI for each of the 40 complete datasets. Then the SAS MIANALYZE procedure will be used to generate statistical inferences by combining results from the 40 analyses using Rubin's formula.

Step 2 and Step 3 will be repeated iteratively until the p-value for treatment effect of dupilumab compared to placebo estimated in Step 4 is >0.05 or the maximum applicable treatment effect has been reached.

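### The FEV1 models adjust for one pre-treatment FEV1 value although two are collected: the analysis is valid but gives up some precision

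*Protocol*

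**What the plan says.** **Collection.** In the schedule of activities (Protocol 1.3.1) the row beginning "Spirometry (pre-BD" is marked at both the screening and the randomization visit. One washout rule covers both: "Spirometry will be performed during a trough period of bronchodilators according to their action duration". Protocol 8.1.1.2 adds: "The same spirometer and standard spirometric techniques, including calibration, will be used to perform spirometry at all visits". SAP Table 7 gives the two readings separate windows, before Day -14 for Visit 1 and from Day -14 up to randomization and first dose for Visit 2.

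**Baseline.** SAP 2.1.1 takes one value for efficacy parameters, "defined as the last available value up to randomization but prior to the first dose of study medication".

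**Models.** The Week 12 MMRM (Protocol synopsis and Table 9; SAP 2.4.4.2.1) includes "baseline pre-bronchodilator FEV₁, and FEV₁ baseline-by-visit interaction as covariates", for ITT and for FeNO ≥20 ppb. For Week 52, SAP 2.4.4.2.2 carries over the Week 12 model: "The change from baseline in pre-bronchodilator FEV₁ at Week 52 will be analyzed in a similar way as change from baseline in pre-bronchodilator FEV₁ at" the earlier time point. The ANCOVA after multiple imputation in SAP Appendix K again uses one value: "smoking status at screening (current smokers or not), and baseline pre-BD FEV₁ value as covariates". Step 1 of that imputation fills intermediate gaps from all visits without saying whether screening is among them; Step 2 lists one baseline value. Nowhere is the screening value named as a second covariate or averaged with Visit 2.

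**Order of testing.** SAP 2.4.4.3 lists eight tests after the primary. The first four are pre-bronchodilator FEV1: Week 12 and Week 52 in ITT, then Week 12 and Week 52 in FeNO ≥20 ppb.

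**The concern.** A single FEV1 reading measures a patient's stable pre-treatment lung function with visit-to-visit noise, and part of that noise stays in the residual of the treatment comparison. A second reading taken before randomization, by the same method, can remove some of it without biasing the comparison.

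The two readings should describe much the same state. The visits are about four weeks apart, background therapy is not to be adjusted during screening (Protocol 6.1.2), and patients with an exacerbation or respiratory infection in that period are excluded (Protocol 5.2, E 07 and E 08).

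The testing order raises the stakes. A miss on any of the four FEV1 tests stops formal testing of SGRQ total score, SGRQ response, E-RS and the FeNO-subgroup exacerbation rate. The sample size was set for exacerbations alone, and no FEV1 power is stated.

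**Working it through.** **The plan's own figure.** The only sample-size figure is for the primary endpoint (Protocol 9.2, SAP 1.3): rates 1.5 and 1.125, follow-up 0.95 year, dispersion 1, two-sided alpha 0.05, 90% power.

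n per arm = (1.960 + 1.282)² × [1/(0.95×1.5) + 1/(0.95×1.125) + 2×1] / (ln 0.75)² = 461.8, so 462, with 90.0% power. The plan's figure is reproduced. It says nothing about FEV1: no SD, correlation, effect size or power is given.

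**Formula for the gain.** Let r1 = corr(Visit 2, outcome), r2 = corr(Visit 1, outcome) and r12 = corr(Visit 1, Visit 2). The residual variance with both readings, relative to Visit 2 alone, is

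ratio = [1 − (r1² + r2² − 2·r1·r2·r12)/(1 − r12²)] / (1 − r1²).

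If all three equal ρ this becomes (1 + 2ρ)/(1 + ρ)².

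**Results. All correlations are assumed.**

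| Case | r12 | r1 | r2 | Ratio | Variance reduction | 462 per arm acts like |
|---|---|---|---|---|---|---|
| Equal, 0.7 | 0.70 | 0.70 | 0.70 | 0.830 | 17% | 556 |
| Equal, 0.8 | 0.80 | 0.80 | 0.80 | 0.802 | 20% | 576 |
| Equal, 0.9 | 0.90 | 0.90 | 0.90 | 0.776 | 22% | 596 |
| Fading | 0.90 | 0.85 | 0.85 | 0.863 | 14% | 535 |
| Fading | 0.90 | 0.80 | 0.80 | 0.906 | 9% | 510 |
| Fading | 0.90 | 0.70 | 0.70 | 0.949 | 5% | 487 |
| Fading, screening weaker | 0.90 | 0.85 | 0.80 | 0.977 | 2% | 473 |
| Autoregressive | 0.90 | 0.85 | 0.765 | 1.000 | 0% | 462 |

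One row in full (0.90, 0.85, 0.80): (0.7225 + 0.64 − 1.224)/0.19 = 0.729, and (1 − 0.729)/(1 − 0.7225) = 0.977.

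**Allowing for age, sex and height,** which are already in the models. If they explain a share c of FEV1 variance, an equal correlation ρ becomes (ρ − c)/(1 − c). With c assumed at 20-50% and ρ at 0.8-0.9, the ratio runs from 0.78 to 0.86.

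**Simulation check.** Over 3,000 null trials with N = 924 per setting, the variance ratios were 0.803 (all 0.8), 0.787 (all 0.9), 0.890 (0.80/0.80 with r12 0.90) and 1.001 (autoregressive). Rejection at the 5% level was 4.7-5.7% with one reading and 4.7-6.0% with two, so neither model loses validity.

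**What this means in ITT.** A further ANCOVA simulation (N = 924; assumed between-patient SD 0.45 L, visit noise 0.13 L, drift 0.05-0.08 L) gave SE 0.01297 L with Visit 2 alone and 0.01178 L with both. The ratio is (0.01178/0.01297)² = 0.82. With Visit 2 alone, 80% power corresponds to a true difference of 2.80 × 0.01297 = 0.036 L, or 36 mL. At an assumed 50 mL, power is about 97% with one reading (50/12.97 − 1.96 = 1.90) and about 99% with two (50/11.78 − 1.96 = 2.28).

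**The case against.** **This is not an error.** The MMRM already adjusts for baseline FEV1, its visit interaction, age, sex, height, region, ICS dose and smoking. Nothing is contradicted or left undefined. This stands in full.

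**The gain is unknown and could be negligible.** The 17-22% figure needs Visit 1 to predict the outcome as well as Visit 2 does. A modest fall in its correlation leaves about 2%, and pure autoregressive decay leaves none. This also stands, with one qualification. Exactly zero requires readings free of visit-level noise. If true lung function decays by a factor φ per week and each reading has reliability a below 1, then r2 − r1·r12 = a(1 − a)φ¹⁶, which is positive.

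**ITT may not need it.** On the assumed SE above, an effect of 50 mL is already well powered. This stands for ITT at Week 12. It does not settle the FeNO subgroup, whose size is not given, or Week 52 after a successful interim, when only participants with the opportunity to reach Week 52 contribute (Protocol 9.4.1, SAP 2.4.4).

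**Stronger readings that a reader might infer.**
- That the screening value never enters an FEV1 model. The last-available rule lets it stand in when Visit 2 is missing.
- That the protocol itself puts four FEV1 tests first. Protocol 9.4.1.1 names only Week 12 FEV1 after the primary; the four-test order is in SAP 2.4.4.3.
- That the covariate choice creates the blocking risk. Blocking comes from the fixed sequence; the covariate only affects the chance of passing each FEV1 step.

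**Conclusion.** The point holds as a loss of efficiency. Two comparable pre-randomization readings are collected, and the FEV1 MMRMs and sensitivity ANCOVAs adjust for one. The planned comparison remains unbiased with type I error controlled, and the primary exacerbation analysis is unaffected.

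The size rests wholly on assumed correlations. At the Week 12 horizon it could lie anywhere in the tabulated range; at Week 52 it is probably lower, because the outcome is further from both readings. The documents do not support calling the FEV1 tests underpowered, nor applying the top of the range to all four. The practical value lies mainly in the FeNO ≥20 ppb tests and the reduced Week 52 set.

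**What to change.** Make the change before any unblinding.

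1. Keep the baseline definition and the change score.
2. In SAP 2.4.4.2.1 and 2.4.4.2.2, add screening pre-bronchodilator FEV1 and its interaction with visit as covariates in the FEV1 MMRMs, for ITT and for FeNO ≥20 ppb.
3. Define the screening value as the last acceptable reading in the Visit 1 window of the screening that led to randomization. This settles retests and rescreened patients.
4. Add the same covariate to the subgroup-interaction MMRM in SAP 2.4.4.2.1 and to the Appendix K imputation and ANCOVA models, so that all FEV1 analyses match.
5. If either pre-randomization reading is missing, fill it from the other by a regression that ignores treatment arm, for covariate use only.

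The cost is SAP wording and one covariate with its interaction, from data already collected; no visit or patient is added. Protocol Table 9 and the synopsis list the present covariates, so the departure should be recorded in SAP 1.6, which now reports no modifications. Aligning the protocol text as well would need an amendment, with the ethics approval that Protocol 10.1.1 requires.
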